5.2. Exclusion Criteria

Participants are excluded from the study if any of the following criteria apply:

Medical Conditions

1. Have known allergies to ramucirumab, any components of the formulation buffer matrix or related compounds, or history of significant atopy

2. Have an abnormal blood pressure (>140/90 mmHg) and/or pulse rate as determined by the investigator
3. Have a history or presence of cardiovascular, respiratory, hepatic, renal, GI, endocrine, hematological, psychiatric, or neurological disorders that could significantly alter the absorption, metabolism, or elimination of drugs; or constituting a risk when taking the study intervention; interfere with the evaluation of injection site assessments, or any other medical condition that, in the judgement of the investigator, could interfere with the interpretation of data
4. Regularly use known drugs of abuse and/or show positive findings on urinary drug/alcohol screening
5. Have evidence of human immunodeficiency virus (HIV) infection and/or positive HIV antibodies
6. Show evidence of hepatitis C and/or positive hepatitis C antibody
7. Show evidence of hepatitis B and/or positive hepatitis B surface antigen
8. Have self-perceived dullness or loss of sensation on either side of the body or the abdomen
9. Have donated blood of more than 500 mL within the previous 30 days of study screening
10. Have a history or presence of a bleeding disorder
11. Have had a serious or nonhealing wound, ulcer, or bone fracture within 28 days prior to enrollment
12. Have undergone major surgery within 28 days, or have postoperative bleeding complications or wound complications from a surgical procedure performed in the last 2 months
13. Have a history of GI perforation, peptic ulceration, diverticular disease, and/or fistulae within 6 months prior to enrollment
14. Have alanine transaminase, aspartate aminotransferase, and gamma-glutamyl transferase > upper limit of normal (ULN)
15. Have bilirubin > ULN
16. Have current or chronic history of liver disease or known hepatic or biliary abnormalities (Gilbert's syndrome is not acceptable)
17. Evidence of hypothyroidism or hyperthyroidism based on clinical evaluation and/or an abnormal thyroid-stimulating hormone that, in the opinion of the investigator, would pose a risk to participant safety. Participants on a stable dose of thyroid replacement therapy for at least the prior 3 months who are clinically euthyroid and who are anticipated to remain on this dose throughout the trial period may be eligible if they meet the other criteria.
18. Have experienced any arterial thromboembolic events, including but not limited to myocardial infarction, stroke, transient ischemic attack, cerebrovascular accident, or unstable angina, \leq 6 months prior to randomization.

Prior/Concomitant Therapy

19. Are currently using aspirin or other nonsteroidal anti-inflammatory drugs

20. Have participated, within the last 30 days, in a clinical study involving a study intervention. If the previous study intervention has a long half-life, 5 half-lives or 30 days (whichever is longer) should have passed.
21. Have previously completed or withdrawn from this study or any other study investigating ramucirumab
22. Have used or intend to use over-the-counter or prescription medication for pain or inflammation within 7 days prior to Day 1 or during the study

Prior/Concurrent Clinical Study Experience

23. Are currently enrolled in a clinical trial involving a study intervention or off-label use of a drug or device, or are concurrently enrolled in any other type of medical research judged not to be scientifically or medically compatible with this trial
24. Have been treated with biologic agents (such as mAbs, including marketed drugs) within 3 months or 5 half-lives (whichever is longer) prior to dosing

Diagnostic Assessments

25. Have tattoos or scars over the abdomen, or other factors (for example, rash, excessive folds of skin) that, in the investigator's opinion, would interfere with injection site assessments

Other Exclusions

26. Are deemed unsuitable for inclusion in the trial in the opinion of the investigator or sponsor
27. Have an average weekly alcohol intake that exceeds 21 units per week (males \leq 65 years old) and 14 units per week (females [and males $>$ 65 years old, if applicable]);
1 unit = 12 oz or 360 mL of beer; 5 oz or 150 mL of wine; 1.5 oz or 45 mL of distilled spirit(s)
28. Are unwilling to stop alcohol consumption during study visits/time in the research unit
29. Smoke more than 10 cigarettes per day or are unable to abide by CRU smoking restrictions

5.3. Lifestyle Considerations

5.3.1. Meals and Dietary Restrictions

There are no dietary restrictions for this study.

5.3.2. Caffeine, Alcohol, and Tobacco

1. During each dosing session, participants will abstain from ingesting caffeine- or xanthine-containing products (for example, coffee, tea, cola drinks, and chocolate) for 24 hours before the start of dosing until after collection of the final PK and/or pharmacodynamic (PD) sample.
2. During each dosing session, participants will abstain from alcohol for 24 hours before the start of dosing until after collection of the final PK and/or PD sample.

3. Participants who use tobacco products will be instructed that use of nicotine-containing products (including nicotine patches) will not be permitted while they are in the CRU.

5.3.3. Activity

1. Participants will abstain from strenuous exercise for 72 hours before each blood collection for clinical laboratory tests. Participants may participate in light recreational activities during studies (for example, watching television, reading).

5.4. Screen Failures

Screen failures are defined as participants who consent to participate in the clinical study but are not subsequently enrolled in the study and were not alternates.

Individuals who do not meet the criteria for participation in this study (screen failure) may be rescreened. Alternates may also be rescreened if out of the screening window. Rescreened participants should be assigned a new participant number. When rescreening, some screening tests and procedures may be repeated at the investigator's discretion. Individuals may be rescreened once only. The interval between rescreenings should be at least 2 weeks. With rescreening, the individual must sign a new ICF. Repeating of laboratory tests once during the screening period or repeating screening tests once to comply with the protocol-designated screening period does not constitute rescreening.

6. Study Intervention

Study intervention is defined as any investigational intervention(s), marketed product(s), placebo, or medical device(s) intended to be administered to a study participant according to the study protocol.

6.1. Study Intervention(s) Administered

Intervention Name	Ramucirumab IV (marketed IV formulation)	Ramucirumab SC	Placebo for SC	Placebo for IV
Type	Drug	Drug	Matching placebo	Matching placebo
Dose Formulation	Vial	Vial	Vial	Vial
Unit Dose Strength(s) ^a	Experimental	Experimental	Placebo	Placebo
Dosage Level(s) ^a	350 mg	350 or 700 mg	NA	NA
Route of Administration ^a	IV infusion (Group 3)	SC injection (Groups 1, 2, 4, 5) SC infusion with a pump (Group 6)	SC injection (Groups 1, 2, 4, 5) SC infusion with a pump (Group 6)	IV infusion (Group 3)
Use ^a	Experimental	Experimental	Placebo	Placebo
IMP and NIMP ^a	IMP	IMP	NIMP	NIMP
Sourcing ^a	Provided centrally by the sponsor	Provided centrally by the sponsor	Provided centrally by the sponsor	Provided centrally by the sponsor
Packaging and Labeling ^a	Study intervention will be provided in a vial. Each vial will be labeled as required per country requirement.	Study intervention will be provided in a vial. Each vial will be labeled as required per country requirement.	Placebo will be provided in a vial. Each vial will be labeled as required per country requirement.	Placebo will be provided in a vial. Each vial will be labeled as required per country requirement.
Current/Former Names or Aliases ^a	Ramucirumab, Cyramza®, LY3009806	Ramucirumab, Cyramza®, LY3009806	Placebo	Placebo

Abbreviations: IMP = investigational medicinal product; IV = intravenous; NA = not applicable;

NIMP = noninvestigational medicinal product; SC = subcutaneous.

a Information provided in this table (dose formulation, sourcing, packaging and labeling, current/former names or aliases) may change throughout the study or may vary by country.

The study intervention will be administered as a slow, IV infusion over at least 60 minutes in Group 3; and as an SC infusion (with a pump) in Group 6 per pharmacy manual; or SC injection in Groups 1, 2, 4, and 5. Sites must have resuscitation equipment, emergency drugs, and appropriately trained staff available during the IV or SC infusion/SC injection and for at least 1 hour after participants have completed the IV or SC infusion/SC injection.

The SC injection site will be the abdomen. The study intervention will be given in the CRU by qualified CRU personnel as designated by the investigator. Study injections should be given by a

limited number of personnel for consistency. The site of administration of each injection will be recorded; when there is more than 1 injection, the same site will not be used but another quadrant will be used.

6.1.1. Special Treatment Considerations

6.1.1.1. Premedication for Infusions and Subcutaneous Injections

Premedication (with IV histamine H₁ antagonists such as diphenhydramine hydrochloride) is planned prior to ramucirumab IV infusion as specified per label for IV administration.

Participants receiving SC infusion/injection will also receive oral premedication such as oral diphenhydramine. After the IV infusion/or SC infusion/injection, a 1-hour observation period will be completed. This will follow the label instructions to be used with the IV marketed material.

Any premedications given will be documented as a concomitant therapy (see Section [6.5](#)).

6.1.1.2. Management of Infusion Reactions

There is a risk of infusion reactions and anaphylaxis with any biological agent; therefore, all participants should be monitored closely. Symptoms and signs that may occur as part of an infusion reaction include, but are not limited to fever, chills, nausea, headache, bronchospasm, hypotension, angioedema, throat irritation, rash, pruritus, myalgia, and dizziness. In the event that a significant infusion reaction occurs, the infusion will be discontinued.

Supportive care should be employed in accordance with the symptoms/signs. Participants should be treated appropriately by the investigator.

In the event of an IRR, every effort should be made to collect a blood sample for an antiramucirumab antibody determination as well as for ramucirumab serum concentration as close to the onset of the reaction as possible, at the resolution of the event, and 30 days following the onset of the event. In the case of generalized urticaria or anaphylaxis, additional blood and urine samples should be collected as described in [Appendix 2](#) (Clinical Laboratory Tests)

6.2. Preparation/Handling/Storage/Accountability

1. The investigator or designee must confirm appropriate temperature conditions have been maintained during transit for all study intervention received and any discrepancies are reported and resolved before use of the study intervention.
2. Only participants enrolled in the study may receive study intervention and only authorized site staff may supply or administer study intervention. All study intervention must be stored in a secure, environmentally controlled, and monitored (manual or automated) area in accordance with the labeled storage conditions with access limited to the investigator and authorized site staff.
3. The investigator, institution, or the head of the medical institution (where applicable) is responsible for study intervention accountability, reconciliation, and record maintenance (that is, receipt, reconciliation, and final disposition records).
4. Further guidance and information for the final disposition of unused study interventions are provided in the Study Reference Manual.

5. Investigators should consult the study drug information provided in the Pharmacy Manual or label for the specific administration information (including warnings, precautions, contraindications, adverse reactions).

6.3. Measures to Minimize Bias: Randomization and Blinding

Study using Precoded Randomization provided to site	
On Day 1, participants will be assigned a unique number (randomization number). The randomization number encodes the participant's assignment to the study, according to the randomization schedule. Each participant will be dispensed study intervention, labeled with his/her unique randomization number, throughout the study.
 
Participants will be sequentially enrolled to groups. Within each group, participants will be randomized to receive a single dose of IV or SC ramucirumab or placebo (7 ramucirumab:3 placebo per group).

--	---

Blinded study with unblinded site pharmacist who is dispensing drug	
Participants will be randomly assigned in a 7:3 ratio (ramucirumab:placebo) to receive study intervention. Investigators will remain blinded to each participant's assigned study intervention throughout the course of the study. In order to maintain this blind, an otherwise uninvolved third party will be responsible for the reconstitution and dispensation of all study intervention and will endeavor to ensure that there are no differences in time taken to dispense following randomization.
 
In the event of a Quality Assurance audit, the auditor(s) will be allowed access to unblinded study intervention records at the site(s) to verify that randomization/dispensing has been done accurately.
 
Blinding will be maintained throughout the conduct of the study as described in the separate Blinding Plan.
 
Emergency codes will be available to the investigator. A code, which reveals the study intervention group for a specific study participant, may be opened during the study only if the participant's well-being requires knowledge of the participant's treatment assignment.
 
If a participant's study treatment assignment is unblinded, the participant must be discontinued from the study, unless the investigator obtains specific approval from an Eli Lilly and Company (Lilly) clinical pharmacologist (CP) or clinical research physician (CRP) for the study participant to continue in the study. During the study, emergency unblinding should occur only by accessing the study participant's emergency code.
 
In case of an emergency, the investigator has the sole responsibility for determining if unblinding of a participant's treatment assignment is warranted for medical management of the event. The participant's safety must always be the first consideration in making such a determination. Where feasible and when timing of the emergent situation permits, the investigator should attempt to contact the Lilly medical monitor before unblinding a participant's treatment assignment. If the investigator decides that unblinding is warranted, it is the responsibility of the investigator to promptly document the decision and rationale and notify Lilly as soon as possible.

--	---

6.3.1. Package and Labeling

Ramucirumab will be provided as a 10-mg/mL (IV) or 175-mg/mL (SC) preservative-free, sterile solution for injection in vials. The Pharmacy Manual will provide instructions for the preparation of 87.5-mg/mL SC ramucirumab. Placebo will be provided as a preservative-free, sterile solution for injection in vials (SC).

Ramucirumab and placebo vials should be stored under refrigeration at 2°C to 8°C (36°F to 46°F) with protection from light.

The study intervention will be labeled according to the country's regulatory requirements

6.4. Study Intervention Compliance

When the individual dose for a participant is prepared from a bulk supply, the preparation of the dose will be confirmed by a second member of the study site staff.

When participants are dosed at the site, they will receive study intervention directly from the investigator or designee, under medical supervision. The date and time of each dose administered in the clinic will be recorded in the source documents and recorded on the case report form (CRF). The dose of study intervention and study participant identification will be confirmed at the time of dosing by a member of the study site staff other than the person administering the study intervention.

6.5. Concomitant Therapy

Participants must abstain from taking prescription or nonprescription drugs (including vitamins and dietary or herbal supplements) within 7 days (or 14 days if the drug is a potential enzyme inducer) or 5 half-lives (whichever is longer) before the start of study intervention until completion of the follow-up visit, unless, in the opinion of the investigator and sponsor, the medication will not interfere with the study.

Acetaminophen, at doses of ≤ 3 grams/day, is permitted for use any time during the study. Premedications for IRRs are permitted for use. Other concomitant medication may be considered on a case-by-case basis, by the investigator in consultation with the Medical Monitor, if possible.

6.6. Dose Modification

If moderate or severe AEs are consistently observed across participants in a group or if unacceptable pharmacological effects, reasonably attributable to ramucirumab administration in the opinion of the investigator, are observed in more than 2 of the participants in a group, then no further participants will be dosed until a full safety review of the study has taken place. Relevant reporting and discussion with the Medical Monitor/Sponsor, relevant personnel, and the Institutional Review Boards (IRBs)/Independent Ethics Committees (IECs) will take place before resumption of dosing.

If the SAE occurs in 1 participant in a group, then dose escalation will be temporarily halted and no further participants will be dosed until a full safety review of the data has taken place. Relevant reporting and discussion with the Medical Monitor, relevant personnel, and the IRB/IEC will take place before resumption of dosing.

Refer to Section 10.3.5 of Appendix 3 for additional information about the sponsor's surveillance process for dose escalation and group expansion.

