4.1. Overall Design

This is a single-site study in healthy participants who will receive a single dose of SC or IV ramucirumab. The study will be participant- and investigator-blinded, randomized, and placebo-controlled (7 ramucirumab:3 placebo per group/dose level). Placebo will be used as a comparator for both IV and SC to allow interpretation of safety and tolerability data following administration.

There will be sentinel dosing in this protocol; the initial 2 participants will be randomized/dosed (1 ramucirumab:1 placebo), and subsequently (the next day), the remaining participants in the group will be dosed. This will be subject to a satisfactory safety review by the investigator. This will occur on the first dose of SC (Group 1).

In Section 4.2, additional rationale is presented for the selection of healthy participants for this investigation.

Participants will be screened within 28 days prior to Day 1 of dosing for each group. Participants will be admitted to the CRU as part of an inpatient visit on Day -1 and will be sequentially enrolled. In each group, participants will be randomized to receive a single dose of IV or SC ramucirumab or placebo (7 ramucirumab:3 placebo per group).

There will be at least a 2-week safety observation period between the titrating SC injection groups (Groups 1 and 2), and between the SC and IV groups (Groups 2 and 3) while local laboratory data is reviewed by the sponsor and investigator. If the safety review is acceptable, Groups 4 and 5 may be dosed simultaneously to Group 3, as no dose escalation is occurring in those groups. Group 6 may be dosed with an infusion pump once the sponsor has reviewed both the safety and PK data (Groups 1 through 3) if the safety results are acceptable and if there is scientific value for investigating an additional group. The dose for Group 6 will be determined (maximum dose 350 mg). The plan for periodic reviews is presented Section 9.5.

The dose levels are provided below and may be adjusted based on safety reviews for preceding groups.

The participants receiving ramucirumab in each group will be administered the following dose level (up to 3 dose levels predicted to be ultimately used for therapeutic intent [see Section 4.3 for dose rationale]):

- **Group 1 will test a ramucirumab 350-mg SC dose**
 - administered at a concentration of 175 mg/mL as 1×2-mL injection.
- **Group 2 will test a ramucirumab 700-mg SC dose**

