 - administered at a concentration of 175 mg/mL as 2×2-mL injections.

- **Group 3 will test a ramucirumab IV dose (maximum of 350 mg)**
 - administered as a 60-minute infusion (maximum 35 mL×10 mg/mL).
 - Analysis of safety and PK data from Groups 1 to 3 will allow initiation of Group 6.
- **Group 4 will test a ramucirumab 350-mg SC dose**
 - administered at a concentration of 87.5 mg/mL as 2×2-mL injections
 - The purpose is to investigate the effect of a different drug product concentration on PK and safety and Group 1 will be the reference comparison group.
- **Group 5 will test a ramucirumab 350-mg SC dose**
 - administered at a concentration of 175 mg/mL as 2×1-mL injections
 - The purpose is to investigate the effect of a different volume administered at the injection site on PK and safety and Group 1 will be the reference comparison group.
- **Optional Group 6 may test SC ramucirumab dose, maximum 350 mg, to further understand SC ramucirumab PK and safety in healthy participants**
 - administered at a concentration of 175 mg/mL administered via an infusion pump according to the pharmacy manual.

The SC injection site will be the abdomen. See Section 6.1 for details.

Following the safety review of Groups 1 and 2, the sponsor and investigator agreed to allow doses to be reduced for remaining groups. This may mean that less groups may need to be studied. The asymptomatic transaminase increases observed during the safety review have also lead to a change in the exclusion criteria to further enhance safety of the participants. In view of these findings, subsequent doses will be capped at 350 mg. Lower doses may also be studied. These decisions will be based on emerging data (see Section 4.3 for further details).

Injection site pain (ISP) and ISRs will be monitored in each group, and a comparison of scorings will be used. The severity of ISP and ISRs reported across all participants will be evaluated. The data from Group 1, in comparison to Groups 4 and 5, will provide insight about the effect of injection volumes and ramucirumab concentration on ISP and ISR.

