8.2.6. Safety Monitoring

The Lilly CP or CRP/scientist will monitor safety data throughout the course of the study. This will include monitoring and recording of all AEs, including all National Cancer Institute Common Terminology Criteria for Adverse Events (CTCAE) version 5.0 grades and SAEs.

The sponsor will review SAEs within time frames mandated by company procedures. The sponsor CP or CRP will periodically review the following data:

- trends in safety data
- laboratory analytes including proteinuria, reduced red blood cells, and decreased neutrophil count
- AEs, including monitoring of AESIs; see Section 8.3.6

When appropriate, the sponsor CP or CRP will consult with the functionally independent Global Patient Safety therapeutic area physician or clinical research scientist.

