9.4.3. Other Safety Analyses

All safety analyses will be made on the Safety Population. The most current version of the Medical Dictionary for Regulatory Activities (MedDRA) at the time of analysis will be used when reporting AEs by MedDRA terms, and CTCAE version 5.0 will be used to assign AE severity grades.

All relevant hematology and chemistry laboratory values will be graded according to CTCAE version 5.0.

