9.5. Interim Analyses

No interim analyses are planned for this study. If an unplanned interim analysis is deemed necessary for reasons other than a safety concern, the protocol must be amended.

However, there will be periodic reviews of data to assess safety, tolerability, and PK data. There will be sentinel dosing in this protocol; the initial 2 participants will be randomized/dosed (1 ramucirumab:1 placebo), and subsequently (the next day), the remaining participants in the group will be dosed. The following information belongs in this section:

- Safety reviews are planned prior to dose escalation after 2-week safety data are available.
- PK data may be reviewed for Groups 1 and 2 if timing permits.
- PK data will be reviewed once Group 1 through 3 PK samples have been collected (cutoff 2-week sample collection in Group 3).

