10.3.3. Recording and Follow-Up of AEs and/or SAEs

AE and SAE Recording

- When an AE/SAE occurs, it is the responsibility of the investigator to review all documentation (for example, hospital progress notes, laboratory reports, and diagnostics reports) related to the event.
- The investigator will then record all relevant AE/SAE information on the CRF.
- It is **not** acceptable for the investigator to send photocopies of the participant's medical records to the sponsor or designee in lieu of completion of the AE/SAE CRF page.
- There may be instances when copies of medical records for certain cases are requested by the sponsor or designee. In this case, all participant identifiers, with the exception of the participant number, will be redacted on the copies of the medical records before submission to the sponsor or designee.
- The investigator will attempt to establish a diagnosis of the event based on signs, symptoms, and/or other clinical information. Whenever possible, the diagnosis (not the individual signs/symptoms) will be documented as the AE/SAE.

Assessment of Intensity

The investigator will make an assessment of intensity for each AE and SAE reported during the study and assign it to 1 of the following categories:

- Mild: An event that is easily tolerated by the participant, causing minimal discomfort and not interfering with everyday activities.
- Moderate: An event that causes sufficient discomfort and interferes with normal everyday activities.
- Severe: An event that prevents normal everyday activities. An AE that is assessed as severe should not be confused with an SAE. Severe is a category utilized for rating the intensity of an event; and both AEs and SAEs can be assessed as severe.
- An event is defined as 'serious' when it meets at least 1 of the predefined outcomes described in the definition of an SAE, NOT when it is rated as severe.
- The investigator will use CTCAE version 5.0 (NCI 2018) to assign AE severity grades.

Assessment of Causality

- The investigator is obligated to assess the relationship between study intervention and each occurrence of each AE/SAE.
- A “reasonable possibility” of a relationship conveys that there are facts, evidence, and/or arguments to suggest a causal relationship, rather than a relationship, cannot be ruled out.
- The investigator will use clinical judgment to determine the relationship.

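### After the 350-mg cap, the pause rule in Protocol 6.6 still lets marked enzyme rises in one or two participants pass without a mandatory pause.

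*Protocol*

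**What the plan says.** Protocol 6.6 has three triggers for halting dosing pending a full safety review. The first two open with "If moderate or severe AEs are consistently observed across participants in a group or if unacceptable pharmacological effects". The adverse-event trigger requires a consistent pattern across a group, with no count. The pharmacological-effect trigger requires more than 2 participants and the investigator's opinion that ramucirumab is the cause. The third is one serious adverse event in a group. None mentions ALT, AST, bilirubin or a multiple of the upper limit of normal (ULN).

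Protocol 4.1 records the signal: "The asymptomatic transaminase increases observed during the safety review have also lead to a change in the exclusion criteria". Protocol 4.3 caps all later doses at 350 mg. The Amendment (c) change table covers dose and exclusion criteria 14 to 16, and does not list 6.6.

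On grading, Protocol 10.3.3 gives an everyday-activities scale ("Mild: An event that is easily tolerated by the participant, causing minimal discomfort and not interfering with everyday activities") and, in the same list, says "The investigator will use CTCAE version 5.0 (NCI 2018) to assign AE severity grades". Protocol 9.4.3 adds: "All relevant hematology and chemistry laboratory values will be graded according to CTCAE version 5.0".

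On reviews, Protocol 9.5 says "Safety reviews are planned prior to dose escalation after 2-week safety data are available". Protocol 4.1 says that, after an acceptable safety review, "Groups 4 and 5 may be dosed simultaneously to Group 3, as no dose escalation is occurring in those groups".

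**The concern.** The trial has already seen the toxicity that matters most to its remaining dosing, and that toxicity came without symptoms. The amendment acted on who may enter and how much they receive. It did not act on what happens if the finding recurs. Group 3 is the first IV dosing in healthy people and has no sentinel pair. If two of its participants show marked enzyme rises, 6.6 does not oblige anyone to hold the next dose, in that group or in Groups 4 and 5. Participants are healthy volunteers with no expected benefit, so a decision of this kind should not rest only on a blinded investigator's judgement.

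**Working it through.** The plan gives no figure to reproduce: the trial is not powered and the documents report no enzyme rates. The check is a reading of the text, followed by illustrative arithmetic.

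**1. Two marked, symptomless ALT rises in Group 3, tested against 6.6.**
- *Before any trigger:* under Protocol 10.3.1 a laboratory change is an adverse event only if the investigator judges it clinically significant.
- *Adverse-event trigger:* graded by CTCAE, the rises may count as moderate or severe. Whether two cases in a group of 10 are a consistent pattern is undefined. A pause is possible but not required.
- *Pharmacological-effect trigger:* two is not more than 2, so it is not met.
- *Serious-event trigger:* not met unless a case is judged serious.

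No trigger must fire.

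**2. Does the cap remove the question?** The Protocol 4.3 table predicts Cmax 211 µg/mL and first-week AUC 18.6 mg.h/mL for 700 mg IV, and 139 and 15.3 for 1400 mg SC. Halving both, which assumes dose proportionality:
- Cmax: 350 mg IV 105.5, 700 mg SC 69.5; ratio 1.52.
- First-week AUC: 9.3 and 7.65; ratio 1.22.
- Total AUC at the assumed bioavailability of 0.6: 350 / (700 × 0.6) = 0.83.

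So predicted early exposure in Group 3 is not below that of the abandoned SC dose, although total exposure is.

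**3. Who could gain.** Groups 4 and 5 hold 2 × 10 = 20 participants, 2 × 7 = 14 of them active. They gain only if dosed after Group 3 results return. The first post-dose chemistry is on Day 2, so none of the 20 gain if all three groups are dosed on one day. Group 6 is optional and already needs a safety and PK review.

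**4. Sensitivity.** Let p be the chance that an active participant exceeds 3 × ULN (assumed), and X ~ Binomial(7, p). For the full enzyme rule (2 or more above 3 × ULN, or any above 5 × ULN), assume that a quarter of rises exceed 5 × ULN, so P = 1 − [(1−p)^7 + 7(0.75p)(1−p)^6].

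| p | More than 2, if every rise counted: P(X ≥ 3) | 2 or more: P(X ≥ 2) | Full enzyme rule |
|---|---|---|---|
| 0.10 | 0.026 | 0.150 | 0.243 |
| 0.20 | 0.148 | 0.423 | 0.515 |
| 0.30 | 0.353 | 0.671 | 0.732 |
| 0.40 | 0.580 | 0.841 | 0.874 |

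The second column is generous to the present rule, since it treats every rise as an unacceptable effect.

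**5. False pauses.** For 10 dosed participants with background rate q above 3 × ULN and q/4 above 5 × ULN (both assumed), P = 1 − [(1−q)^10 + 10(0.75q)(1−q)^9].

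| q | Calculation | P |
|---|---|---|
| 0.005 | 1 − (0.9511 + 0.0358) | 0.013 |
| 0.01 | 1 − (0.9044 + 0.0685) | 0.027 |
| 0.02 | 1 − (0.8171 + 0.1251) | 0.058 |
| 0.05 | 1 − (0.5987 + 0.2363) | 0.165 |

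The bilirubin trigger is left out because the documents give no rate for it; any effect would be to raise these figures.

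**The case against.** The strongest reply is that the plan already has layered liver oversight, and that it worked. Safety review of Groups 1 and 2 found symptomless rises, and the response was a cap, tighter exclusions and an optional Group 6. Liver injury is an event of special interest (8.3.6), the investigator must review every laboratory report (8.2.4), 9.5 also promises periodic data reviews in general terms, and 10.3.5 describes sponsor surveillance. All of that stands. A reader might infer that the liver goes unwatched; the documents do not support that. What they lack is a level at which dosing must stop.

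A reader might also infer that two severity scales give opposite answers, so that a symptomless rise is always mild. That is too strong. CTCAE v5.0 is required in the Schedule of Activities, Protocol 8.2.6, 8.3, 9.4.3 and 10.3.3, and SAP 9.4.1. The missing mapping in 10.3.3 is a drafting gap.

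Nor are Groups 4 and 5 ungated. Their simultaneous dosing depends on an acceptable safety review, and they repeat a dose level that 4.3 calls acceptable. The narrower fact is that no review is required between them and Group 3. If the 2-week observation in the synopsis is read to cover them, even that gap closes.

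The analytes named in 8.2.6 ("laboratory analytes including proteinuria, reduced red blood cells, and decreased neutrophil count") omit transaminases, but the list is not exhaustive, and the section also covers safety trends and special-interest events. Changing it would be editorial.

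Finally, the event rates and ULN multiples are assumptions. That is correct, and it limits what the arithmetic can show.

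**Conclusion.** The concern holds in a limited form. Section 6.6 is not listed as changed after the finding that ended 700-mg dosing, and as written it does not require a pause for marked enzyme rises in one or two participants. The other safeguards are real but depend on judgement, and none is required to operate between Groups 3, 4 and 5. The scale question is minor.

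The gain is small: at most 20 participants (14 active), plus replacements and any dosing staggered within a group, and nil for anyone dosed before results return. The conclusion about 6.6 rests on the text alone. The firing and false-pause probabilities rest on assumed rates, on the assumption that a quarter of rises above 3 × ULN exceed 5 × ULN, and on independence between participants. The change is worth making because it protects healthy volunteers at very low cost.

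**What to change.** Amend Protocol 6.6 in two places.

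1. State that laboratory adverse events are judged by CTCAE v5.0 grade, with moderate meaning grade 2 and severe meaning grade 3 or higher.
2. Add that dosing stops until a full safety review is complete if, after dosing and with or without symptoms:
   - (a) ALT or AST exceeds 3 × ULN in 2 or more participants in a group;
   - (b) ALT or AST exceeds 5 × ULN in any participant; or
   - (c) ALT or AST exceeds 3 × ULN with total bilirubin above 2 × ULN in any participant.

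Count every dosed participant, active or placebo, so that no unblinding is needed. The levels are examples, and the sponsor should confirm them against the Groups 1 and 2 data, which the documents do not give.

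The cost is a few lines by amendment. ALT, AST and bilirubin are already in the Appendix 2 panel and are drawn repeatedly from Day 2. The operational downside is an occasional temporary pause for an unrelated rise, at the rates shown in step 5. No change to 8.2.6 is needed.
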